**iv. Primary Outcome**

- Duration of sensory block – defined as time from end of injection to first sensation of pain at surgical site

**v. Secondary Outcomes**

- Time to first opioid consumption – from end of injection to time to first oral opioid consumption
- Duration of motor block - from end of injection to time of baseline preoperative biceps and hand strength
- Oxygen saturation on room air 1 hour after arrival to recovery room
- Opioid consumption on POD 1 at 12 hours/bed time if patient retires to bed before the 12hr time point), 24 hours and 7 days
- NRS for pain at 12hrs/Bed time (if patient retires to bed before the 12hr time point), 24hours, 7 days
- Blood glucose in recovery room
- Persistent paresthesia in the operative arm at 7 days
- Localized infection at block site at 7 days
- Postoperative nausea

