laryngeal mask airway can be placed for spontaneously breathing patients. Anesthesia will be maintained using the inhalational anesthetic sevoflurane (AbbVie) with an end-tidal concentration of 1.4 - 2%. The surgeon will infiltrate the arthroscopic port insertion sites with 10-40ml total volume of bupivacaine 0.25% (1:200,000 epinephrine) or lidocaine (as determined by the attending physician). Muscle relaxation will be reversed using a combination of neostigmine (0.04mg/kg) and glycopyrrolate (0.007mg/kg) if necessary. Standard anti-emetic prophylaxis with the serotonin antagonist ondansetron (4mg) will be given. For the purpose of this study, patients will not receive additional dexamethasone regardless of group allocation.

Upon arrival to the recovery room, pain (Verbal Response Score  $\geq 4$  or patient request for analgesia) will be treated with intravenous hydromorphone (solely for this study) in 0.2-0.4mg increments every 5 minutes as needed. Postoperative nausea will be treated (as needed) with an additional dose of ondansetron (1mg), droperidol (0.625mg), dimenhydrinate (50mg) or prochlorperazine at the discretion of the attending physician. Capillary blood glucose will also be assessed and recorded for this study. Once oral intake is initiated, patients will receive one of several analgesic preparations as needed: Tylenol #3® (acetaminophen 325 mg/codeine 30 mg/cafeine 15 mg per tablet), or oxycocet (acetaminophen 325 mg/oxycodone HCl 5 mg per tablet), oxycodone 5-10 mg, or hydromorphone 2-4 mg if intolerant to codeine at the discretion of the attending physician. Upon discharge from hospital, patients will receive a prescription for Tylenol #3® as needed, or hydromorphone or oxycocet if intolerant to codeine at the discretion of the attending physician.

After discharge, patients will complete a home pain diary with information that will be collected by research personnel during postoperative telephone calls. Patients will be asked to record the time at which they first experience pain at the surgical site, the time when they first consumed prescribed opioid

analgesics for surgical site pain and when they regained preoperative baseline hand strength.

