Postoperatively patients will be requested to document interval oral analgesic consumption, presence of nausea or vomiting, presence of weakness in the operative arm, and presence of paresthesia (numbness or tingling) in the operative arm. The doses of oral codeine, hydromorphone, or oxycodone consumed by each patient will be converted into equianalgesic doses (oral morphine equivalents). Conversion ratios will be employed according to the general monograph for opioids in the Canadian Pharmacists' Association Compendium of Pharmaceuticals and Specialties (36th ed., 2001) as follows: oral oxycodone: oral morphine sulphate = 1:1.5, oral hydromorphone:oral morphine sulphate = 1:5, and oral codeine: oral morphine sulphate = 6.6:1. The Opioid conversion table has been appended to this protocol.

All patients will be followed-up by telephone on post operative days 1 and 7 (+/- up to 5 days depending on patient availability) to collect the following study data: NRS pain scores, onset of pain and return of the affected hand to normal strength; side effects or complications experienced [(e.g. paresthesia - numbness or tingling, infection at ISB site) in the operative arm, and whether the numbness or tingling was located distal or proximal to the operative site]; and, the quantity, frequency and onset of opioid consumption.

Additional information will not be asked, however if an adverse event (AE) was mentioned during telephone follow-up visits, this will be documented in the AE log and assessed accordingly by the QI.

Additional follow-up telephone visits may be conducted as required in the event of a Serious Adverse Event (SAE) or Adverse Reaction (AR) and will be reported in accordance with the Site Guidance on Safety Reporting document

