### Data collection plan

Data will be collected according to the Source-CRFs/CRFs. All data collection will be conducted by a research staff member, either a research assistant or a co-investigator, who is blinded to the patient's treatment allocation.

1. Identifying information, exclusion criteria, surgical procedure description and anesthesia data will be collected preoperatively.
2. Procedure details, including: sedative used, procedure duration (end of injection), pain on injection and the presence of blood will be collected during the block procedure.
3. Pinprick sensation in the C4-T1 dermatomes at 10 and 20 minutes post block (to characterize presence/absence of block). Pain Sensation is characterized as a: (2) = sharp sensation, (1) = dull sensation only, or (0) = no sensation.
4. Motor function (elbow flexion for biceps) at 10 and 20 minutes post block. Power is graded using (2) = normal movement, (1) = reduced movement and (0) = no movement.
5. Intra-operative anesthesia data collection. Time of first Incision, administered anesthesia and time procedure ended.
6. Room air pulse oximetry 1 hour after admission to PACU/recovery room (to characterize respiratory function near discharge)
7. Blood Glucose level in PACU.
8. An account of analgesia administered in PACU.
9. Numerical rating scale (NRS) pain scores 1 hour after admission to PACU to PACU/recovery room
10. Information regarding post block complications (including pain and bruising around the block site) will be collected in a 1 week postoperative telephone call with the patient.
11. Time to first pain sensation in the shoulder, analgesic use and return of the affected hand to normal strength will be captured in the take home patient diary and reported at follow-up telephone calls.
12. NRS pain scores, analgesia consumption and side effects experienced will be captured at: 12hours/bed time, 24 hours and 7 days post-operatively in the patient's diary reported at follow-up telephone calls.

Upon achieving enrolment of the specified 180 patients and data is collected, the database will be verified, and analyzed by the biostatistician.

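### Motor block duration is defined by recovery of biceps and hand strength, but the plan describes collecting a recovery time for the hand only

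*Combined protocol and SAP*

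**What the plan says.** Section E.v defines the duration of motor block as "from end of injection to time of baseline preoperative biceps and hand strength". Section E.vii analyses it as a time, by the same two-sample equivalence test of means as the primary outcome.

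The descriptions of what is collected are these:

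- Home diary (section E.iii, Protocol): patients record "when they regained preoperative baseline hand strength".
- Telephone calls on postoperative days 1 and 7 (section E.iii): the items include "NRS pain scores, onset of pain and return of the affected hand to normal strength". Apart from adverse events that a patient happens to mention, the calls go no further: "Additional information will not be asked".
- Data collection plan, item 11 (section E.viii): "Time to first pain sensation in the shoulder, analgesic use and return of the affected hand to normal strength will be captured" in the diary and reported at the calls.
- Data collection plan, item 4: "Motor function (elbow flexion for biceps) at 10 and 20 minutes post block", graded 0 to 2.
- Postoperative patient record (section E.iii): "presence of weakness in the operative arm" is also documented.

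**The concern.** The definition needs the moment at which two muscle groups are both back to baseline. Each of the three places that describe a recovery time names only the hand. The biceps, which the plan uses to grade motor block in the block room, has no described recovery time. An analyst following the plan would compute hand recovery and report it under a biceps-and-hand label. What is at stake is the meaning of one secondary endpoint. A recovery time that was never asked for also cannot be reconstructed reliably once follow-up is over.

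**Working it through.** **1. Definition against collection.**

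| Place | What is obtained | Covers biceps? | Gives a recovery time? |
|---|---|---|---|
| E.v, definition | Return of biceps and hand | Required | Required |
| E.iii, diary | Return of hand | No | Yes |
| E.iii, calls | Return of hand | No | Yes |
| E.viii, item 11 | Return of hand | No | Yes |
| E.viii, item 4 | Elbow flexion grade at 10 and 20 minutes | Yes | No |
| E.iii, arm weakness | Present or absent | Not separately | No |

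No collection row answers yes in both columns.

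**2. What the recorded value is.** Measure times from the end of injection. Let B be the time the biceps returns to baseline and H the time the hand does.

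- Defined duration: D = max(B, H)
- Recorded duration: R = H
- Shortfall: D − R = max(0, B − H), which is never negative

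R equals D when the hand recovers last or both recover together. Otherwise R is too short by B − H. If a share q of patients have the biceps recovering last, by m hours on average, the mean shortfall is q × m. The documents give neither q nor m.

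**3. Can the early biceps grades supply B?** No. Section E.vi expects a mean sensory block of 12 hours, rising to 18 hours with perineural dexamethasone. No motor duration is stated. On the assumption that motor block also lasts for hours, grades at 10 and 20 minutes describe onset only.

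**4. Can the arm-weakness entry supply D?** Not as a time. Suppose it is recorded at the diary points that item 12 lists for side effects (12 hours or bedtime, 24 hours, 7 days); this is an assumption. It would then place recovery only within an interval of about 24 − 12 = 12 hours, or 7 × 24 − 24 = 144 hours. The only equivalence margin in the plan, set for the primary outcome, is 2 hours. The entry also cannot separate biceps from hand.

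**5. Effect on the comparison between arms.** With S for the mean shortfall in each arm:

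recorded difference = defined difference − (S experimental − S control)

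If the shortfalls are equal, the difference in means is unchanged. If they differ, it moves by an amount and in a direction that the documents do not give.

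**6. Is the primary calculation touched?** The plan's 87 per group can be reproduced by two one-sided tests with margin 2 hours, SD 4 hours, one-sided α of 0.05, true difference zero and 90% power: n = 2 × [4 × (1.645 + 1.645) / 2]² = 86.6, rounded up to 87. No motor outcome enters it.

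**The case against.** The strongest reply is that the forms themselves are not in the documents. Section E.viii says the home diary will capture every outcome not obtained in hospital, and it lists motor block assessments among the source forms. A biceps recovery item could exist there. This stands as a limit: the point concerns what the protocol describes. It does not remove the mismatch, because three separate descriptions agree on the hand alone and the calls are said to ask nothing more. If a form does hold such an item, the text still needs to be aligned with it.

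It is also fair to say that arm weakness is recorded, so elbow weakness after discharge is not wholly unobserved. That is why the point is limited to recovery times.

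A third reply is that hand strength is a sensible measure for patients to report at home. It may be, but section E.v does not define the outcome that way.

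Finally, this is one secondary outcome and both arms are measured alike, so it could be called a wording matter. The limited weight is right. But the choice between one muscle group and two changes what the outcome measures, so it is more than missing detail.

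A reader might go further and infer that the equivalence test on motor duration would succeed falsely because the hand is hardly blocked. The documents do not support that. They say nothing about how often the hand is spared or which muscle recovers first, and step 5 shows that the effect on the arm difference has no known sign.

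**Conclusion.** The mismatch holds. As described, the recorded motor block duration is the hand time. It cannot exceed the defined duration, and it falls short in any patient whose biceps recovers after the hand. The direction follows from the definition, reading it as requiring both muscle groups; the size and the share of patients affected cannot be derived.

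All 180 planned patients lack a described biceps recovery time. A reader might infer that all 180 durations would be wrong, but that does not follow, since the two durations agree wherever the hand recovers last. The conclusion assumes that the unseen forms match the protocol's descriptions of them.

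This concerns one of nine listed secondary outcomes, and one of the two time-based ones that section E.vii names for the equivalence test. The primary outcome, its test and the sample size are unaffected. The change is worth making because it is nearly free before data are collected.

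**What to change.** Add one item to the home diary and the call script: the time at which bending the elbow felt as strong as before surgery. Define motor block duration in section E.v as the later of the elbow-flexion and hand times, and carry this into section E.iii, section E.vii and item 11 of the data collection plan. The cost is one more patient-reported item and no extra visit.

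If that is not wanted, redefine the outcome in section E.v as the time to patient-reported return of hand strength, and name it so in section E.vii. This costs only wording, but gives up any claim about biceps recovery.

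A hand-grip check at 10 and 20 minutes would not be a substitute. It describes early onset and cannot show that a hand was never weak, because weakness could develop later.

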**ii. Exclusion Criteria**

1. Lack of patient consent (including: inability to read or understand the ICF)
2. Allergy to dexamethasone or ropivacaine
3. BMI  $>$  35 kg/m^2

4. Contraindications to low dose dexamethasone including peptic ulcer disease, systemic infection, glaucoma, active varicella/herpetic infections, diabetes mellitus
5. Contraindications to ISB including severe Chronic Obstructive Pulmonary Disease (Forced expiratory volume < 40% predicted), coagulopathy, pre-existing neurologic deficit in ipsilateral upper extremity, localized infection
6. Pregnant or nursing females
7. Chronic opioid use defined as > 30mg oral morphine or equivalent per day
8. Unable to take acetaminophen or celecoxib

iii. **Protocol**

Patients scheduled for arthroscopic shoulder surgery will be approached for participation by research assistants in the pre-operative anesthetic clinic. Patients providing informed consent will be allocated 1:1 in blocks of 10 using a computer generated random number table (randomization will be stratified by site) and blinding of group allocation will be maintained with sequentially numbered, sealed, opaque envelopes.

**The following paragraph outlines standard of care practice (unless otherwise stated) for patients undergoing arthroscopic shoulder surgery at HoAC:**

On the day of surgery, patients will be pre-medicated with oral acetaminophen 1000mg, and oral celecoxib 400mg, unless otherwise stated by the attending physician. Once intravenous access is secure and standard monitors applied (electrocardiogram, non-invasive blood pressure cuff, continuous oxygen saturation), patients will receive sedation with intravenous midazolam (1-2mg). The lateral aspect of the neck including the supraclavicular fossa ipsilateral to the surgical site will be cleansed with standard isopropyl alcohol/chlorhexidine gluconate solution. The US-guided ISB will be performed under sterile conditions by a staff regional anesthesiologist, regional anesthesia fellow, or residents under supervision.

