**vii. Statistical analysis**

Demographic data will be summarized and expressed using appropriate measures of central tendency and dispersion for continuous data, means and standard deviations will be provided (medians and interquartile ranges for non-normally distributed data) and for categorical data counts and percentages will be displayed. The primary outcome, time to first sensation of pain at the surgical site, will be compared between the two groups using a two sample equivalence test of means. Secondary outcomes that are time based will also be assessed in the above manner (time to first analgesic request, duration of motor block). Continuous secondary outcomes (opioid consumption, NRS) will be assessed with repeated measures ANOVA while blood glucose will be assessed with the t-test. Categorical outcomes (paresthesia,

infection, nausea) will be compared with the Chi square or Fisher's exact test for the case of low expected cell counts.

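### Recovery-room SpO2 has no pre-block value listed for collection and no analysis method named, so an inexpensive gain in precision is given up

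*Combined protocol and SAP*

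**What the plan says.** Section E.v lists "Oxygen saturation on room air 1 hour after arrival to recovery room" among the secondary outcomes. Item 6 of the Data collection plan matches it and adds a purpose: "Room air pulse oximetry 1 hour after admission to PACU/recovery room (to characterize respiratory function near discharge". This is the only saturation reading listed for collection.

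The monitor is in place well before that. Section E.iii has "standard monitors applied (electrocardiogram, non-invasive blood pressure cuff, continuous oxygen saturation), patients will receive sedation with intravenous midazolam", and the block comes after this. The two collection items covering that period do not name saturation. Item 1 reads "Identifying information, exclusion criteria, surgical procedure description and anesthesia data will be collected preoperatively", and item 2 covers "Procedure details, including: sedative used, procedure duration (end of injection), pain on injection and the presence of blood".

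On analysis, section E.vii says "Continuous secondary outcomes (opioid consumption, NRS) will be assessed with repeated measures ANOVA while blood glucose will be assessed with the t-test". It also assigns methods to the time-based outcomes and to paresthesia, infection and nausea. SpO2 is the one listed secondary outcome with no method. No baseline adjustment is described for any outcome.

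Glucose appears in item 7 of the Data collection plan as "Blood Glucose level in PACU", without a clock time.

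**The concern.** Starting saturation is likely to differ between patients. The trial admits ASA class I to III and BMI up to 35 kg/m², and excludes COPD only when it is severe (forced expiratory volume below 40% predicted). If the 1-hour readings are compared alone, that between-patient spread stays in the error term. A reading taken from a monitor that is already attached could remove part of it.

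There are two related gaps. With no method named for SpO2, the analyst would have to choose one after the data exist. There is also no rule for a patient who has no room-air reading at 1 hour.

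At stake is the precision and pre-specification of one secondary outcome.

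**Working it through.** **1. The plan's own sample size.** The documents give no SD, power or target difference for SpO2, so the only stated figure to reproduce is the primary one in E.vi: SD 4 h, margin 2 h, α = 0.05, and 0.9 (printed as β, read here as power). For two one-sided tests with a true difference of zero:

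n per group = 2 × [SD × (z₀.₉₅ + z₀.₉₅) / margin]² = 2 × [4 × (1.645 + 1.645) / 2]² = 86.6, rounded up to 87.

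This matches the stated 87 per group. It is used below only as the number analysed.

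**2. Single 1-hour value, no baseline.** For a two-sided 0.05 test with 80% power, in SD units:

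detectable difference = (1.96 + 0.84) × √(2/87) = 0.425 SD.

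With all 90 recruited per group it is 0.418 SD.

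**3. With ANCOVA on a pre-sedation value.** Residual variance is multiplied by (1 − r²), where r is the correlation between the baseline and 1-hour values. The detectable difference is multiplied by √(1 − r²), and the equivalent number per group is 87 / (1 − r²). The documents do not give r, so a range is assumed.

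| Assumed r | Variance cut (r²) | Detectable difference, 80% power | Power at 0.425 SD | Equivalent n per group |
|---|---|---|---|---|
| none | 0% | 0.425 SD | 80.0% | 87 |
| 0.3 | 9% | 0.405 SD | 83.6% | 96 |
| 0.5 | 25% | 0.368 SD | 89.9% | 116 |
| 0.7 | 49% | 0.303 SD | 97.5% | 171 |

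**4. Why not a change score.** If the SD is the same at both times, a change score has variance 2(1 − r) relative to the single value: 1.4, 1.0 and 0.6 at r = 0.3, 0.5 and 0.7. ANCOVA gives 0.91, 0.75 and 0.51. The change score is less precise than ANCOVA at each of these correlations, and below r = 0.5 it is worse than having no baseline.

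**5. Scale.** If the SD of SpO2 were 2 percentage points (assumed), the detectable differences would be 2 × 0.425 = 0.85 points without a baseline and 0.81, 0.74 or 0.61 points with one.

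**The case against.** The strongest reply is that this is a refinement. On the assumed SD of 2 points, the unadjusted comparison already detects less than one saturation point, and adjustment moves it by 0.04 to 0.24 points. SpO2 values sit near a ceiling, so r may be low and the gain close to the 9% row. Item 6 states its purpose as describing respiratory function near discharge, which is a level and needs no baseline. A pre-block value may also be on a preoperative CRF that the documents do not show. All of this stands and limits the size of the point. It does not supply an analysis method, and even if a baseline is recorded somewhere, nothing says it will be used.

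Several stronger readings are tempting, and the documents do not support them:

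- *The comparison is biased.* Allocation is randomised 1:1, so low starting values are balanced in expectation. Only precision is lost.
- *The low-volume rationale is left untested for want of a baseline.* Both arms receive the same volume of 0.5% ropivacaine, so the contrast between arms cannot test low against high volume, with or without adjustment.
- *SpO2 has been assigned an impossible repeated measures ANOVA.* That sentence names only opioid consumption and NRS. The gap is that no method is named.
- *The most affected patients are dropped.* The plan does not say so. It is silent on patients who cannot be measured on room air at 1 hour, and it gives no frequency.
- *Glucose is sampled after oral intake, or needs a baseline.* E.iii does not say that sampling follows oral intake; its glucose sentence comes before the one on starting intake. Diabetes is an exclusion, which narrows the starting spread. What is missing is a stated time. Fixing it at 1 hour after PACU arrival would still not fix the interval from dexamethasone, because surgery length varies.

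**Conclusion.** The point holds as a modest one about precision and pre-specification. The 1-hour SpO2 outcome has no listed pre-block value and no named analysis, while the means of obtaining a baseline is already attached to the patient. Adjustment would cut residual variance by 9% to 49% and lower the detectable difference from 0.425 SD to between 0.405 and 0.303 SD at 87 per group.

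Those figures assume r between 0.3 and 0.7, a linear relation between baseline and outcome, and 87 analysable patients per arm. The documents support none of the r values in particular, and the ceiling on SpO2 points to the lower end. Naming a method and a rule for missing room-air readings is worth doing even if r proves small. The primary equivalence conclusion is unaffected.

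**What to change.** 1. Add one field to the Data collection plan: SpO2 on room air, read from the monitor already in place, before midazolam. The protocol does not say whether the pre-sedation reading is taken on room air, so the field must specify it.
2. Add to E.vii: *Room-air SpO2 at 1 hour will be compared between groups by ANCOVA with the pre-sedation room-air value as covariate, reporting the adjusted mean difference with a 95% confidence interval.* Do not use a change score.
3. Add a CRF flag for patients not measurable on room air at 1 hour, and a rank-based sensitivity analysis that gives them the worst rank. The safety log cannot stand in for this flag, because E.ix lists saturation below 90% among events that the QI need not assess and record.
4. Optional and minor: record the clock time of the PACU glucose sample.

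The cost is a few CRF fields, a brief room-air reading before sedation and two analysis sentences. No new device, visit or blood sample is needed. The downside is that the gain may be small, on a secondary outcome.

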**vi. Sample size calculation**

Based on our clinical experience with low dose US-ISB (ropivacaine 0.5% 5ml) as well as previously published work, we expect mean sensory block duration of 12 hours with a standard deviation of 4 hours.

Based on the literature, we expect a mean prolongation of block time associated with perineural dexamethasone to be approximately 50% thereby increasing block duration to 18 hours. Defining an equivalency margin of 2 hours, we estimate that 87 patients per group (174 total) will be required to reliably test our hypothesis given  $\alpha=0.05$  and  $\beta=0.9$ . To account for incomplete data or loss to follow-up, the plan is to recruit 90 patients per group (180 total).

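### The first opioid-consumption total stops at bedtime if that comes before 12 hours, so the 12 h entry is not consumption over 12 hours (minor; one time point of a secondary outcome)

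*Combined protocol and SAP*

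**What the plan says.** Section E.v (Secondary Outcomes) defines the consumption outcome as "Opioid consumption on POD 1 at 12 hours/bed time if patient retires to bed before the 12hr time point), 24 hours and 7 days". The NRS pain outcome in the same list carries the same bedtime alternative.

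Item 12 of the Data collection plan (section E.viii) repeats it for both measures: "NRS pain scores, analgesia consumption and side effects experienced will be captured at: 12hours/bed time, 24 hours and 7 days post-operatively".

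Section E.iii (Protocol) describes what the diary holds: "Postoperatively patients will be requested to document interval oral analgesic consumption". The follow-up telephone calls collect "the quantity, frequency and onset of opioid consumption". The clock time of the first opioid dose is asked for; the clock time of later doses is not mentioned.

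Section E.vii (Statistical analysis) states: "Continuous secondary outcomes (opioid consumption, NRS) will be assessed with repeated measures ANOVA". Nowhere does the plan say that the length of the first window is recorded, that the total is standardised to it, or that doses taken between bedtime and 12 h are assigned back to the first window.

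**The concern.** NRS and opioid consumption are different kinds of measurement under one timing rule. If a patient is asleep at 12 h, taking the pain score at bedtime is a reasonable substitute. Consumption is a sum over time: its first window becomes the shorter of 12 h and the time to bedtime, and therefore differs between patients.

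Two hypothetical patients show the effect. Each has a block that ends 11 h after injection and then takes two 30 mg codeine tablets. At the plan's 6.6:1 ratio this is 60/6.6 = 9.1 mg oral morphine equivalent.

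- Patient A is injected at 09:00, takes the tablets at 20:00 and goes to bed at 22:30. The 12 h entry is 9.1 mg.
- Patient B is injected at 13:00, goes to bed at 22:30 (9.5 h), wakes in pain at midnight (11 h) and takes the tablets. The 12 h entry is 0, and the 9.1 mg goes to the 24 h entry.

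The two differ only in their slot on the operating list. At stake is whether the reported 12 h figure means what its label says, and whether the pattern over time in the repeated measures analysis reflects opioid use or partly the hour of surgery.

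**Working it through.** **The plan's own figure.** The plan gives no figure for opioid consumption. Its sample size does not depend on this point, but it reproduces. From section E.vi: "Defining an equivalency margin of 2 hours, we estimate that 87 patients per group (174 total) will be required". Two one-sided tests at 0.05 each, SD 4 h, true difference 0 and 90% power give n = 2 × (4/2)² × (1.645 + 1.645)² = 8 × 10.82 = 86.6, or 87 per group.

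**Step 1: window length.** First window = min(12, bedtime − clock start). The following interval, to 24 h, is 24 minus that. The documents give no operating or bed times, so these are illustrations for bedtimes from 20:00 to 24:00:

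| Clock start | First window (h) | Interval to 24 h (h) |
|---|---|---|
| 08:00 | 12 | 12 |
| 10:00 | 10 to 12 | 12 to 14 |
| 12:00 | 8 to 12 | 12 to 16 |
| 14:00 | 6 to 10 | 14 to 18 |
| 16:00 | 4 to 8 | 16 to 20 |

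**Step 2: share of patients with a shortened window.** Assume injection uniform over 08:00–15:00, bedtime normal around 22:30 with SD 1 h, and the clock starting at end of injection. With bedtime at 22:30, the window is short when injection is after 10:30: (15 − 10.5)/7 = 64%. Simulation including the spread of bedtimes also gives 64%, with a mean window of 10.5 h and a 10th percentile of 8.0 h.

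**Step 3: when blocks end.** Section E.vi says "we expect mean sensory block duration of 12 hours with a standard deviation of 4 hours" for the low-dose block, and with perineural dexamethasone a prolongation of "approximately 50% thereby increasing block duration to 18 hours". Take block end as normal with SD 4 h, carrying that SD to 18 h as an assumption.

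- Blocks ending by 12 h: Φ((12 − 18)/4) = Φ(−1.5) = 6.7% at mean 18 h; Φ(0) = 50% at mean 12 h.
- With bedtime at exactly 10 h, blocks ending between 10 and 12 h: at mean 18 h, 6.7% − Φ(−2) = 6.7% − 2.3% = 4.4% of all patients; at mean 12 h, 50% − Φ(−0.5) = 50% − 30.9% = 19.1%.

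**Step 4: opioid moved out of the 12 h entry.** Combine steps 2 and 3 and assume, for illustration only, two 30 mg codeine tablets (9.1 mg) at block end and every 4 h afterwards. Simulated results per patient, in mg oral morphine equivalent:

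| Mean block duration | Patients with a displaced dose | True 0–12 h mean | Recorded mean | SD, true → recorded |
|---|---|---|---|---|
| 18 h | about 3% | 0.66 | 0.39 | 2.58 → 1.99 |
| 12 h | about 20% | 6.2 | 4.3 | 7.23 → 6.44 |

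The mean loss is 0.66 − 0.39 = 0.27 mg at 18 h and 6.2 − 4.3 = 1.9 mg at 12 h. One 30 mg codeine tablet is 30/6.6 = 4.5 mg.

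**Step 5: what does not change.** The sum of the first two intervals still covers 0–24 h. If the 24 h entry is in fact cumulative, it is already correct and only the 12 h entry is short.

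**The case against.** The strongest reply is that the effect is small and falls where little depends on it. Most of this stands.

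- **Size.** In relative terms the recorded mean is 59% (mean 18 h) or 70% (mean 12 h) of the true value, and a reader might infer a large loss. At 18 h the base is tiny: only 6.7% of blocks end by 12 h, and the absolute loss is 0.27 mg. The larger effect needs a 12 h mean, which is the plan's figure before any dexamethasone effect. Both arms receive dexamethasone, so 12 h is a lower bound on duration.
- **Bias.** A reader might infer that the comparison of routes is distorted. Allocation is randomised, stratified by site and blinded, and the rule is the same in both arms. Pain could shift bedtime, but nothing in the documents shows that it does so differently by arm.
- **Noise.** A reader might expect unequal windows to make the outcome noisier. In the illustration the absolute SD falls; only variation relative to the smaller mean rises.
- **Early block failure.** A reader might infer that early failures go undetected. First pain (the primary outcome) and time to first opioid both run from end of injection. Patients A and B would each score 11 h on both.
- **Clock start.** The durations run from end of injection, while item 12 of the Data collection plan speaks only of post-operative hours. A later start would shorten more windows, but the wording may be loose and the documents give no interval between injection and end of surgery. This is a separate ambiguity.
- **Recoverability.** The diary form is not in the documents. It may hold dose times from which a true 0–12 h total could be rebuilt, so it is not established that the information is lost.
- **Disclosure.** The bedtime alternative is stated openly, so consumption to 12 h or first bedtime is a disclosed quantity. It is still not a common window, and the analysis section treats it as one time level.

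**Conclusion.** The point holds as a minor measurement error at one of the three time points of one secondary outcome. Followed as written, the plan yields a 12 h opioid figure that covers less than 12 h for anyone who goes to bed sooner. The figure is therefore too low and depends on the hour of surgery. Under interval recording, the displaced doses inflate the 24 h entry.

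That the window varies follows from the text alone. The size rests on assumed injection times, bedtimes and dosing, on normal block durations with SD 4 h, and on a clock from end of injection. On those assumptions about 64% of windows are short, but a dose is displaced in only about 3% of patients at a mean duration of 18 h, and in about 20% at the 12 h lower bound.

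The documents do not support a claim of directional bias between arms, of reduced precision, or of any effect on the primary outcome, the sample size, time to first opioid, or the cumulative 24 h and 7-day totals.

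**What to change.** In section E.v and in item 12 of the Data collection plan, keep the bedtime alternative for the NRS score only. Define opioid consumption as oral morphine equivalents taken in fixed windows from end of injection (0–12 h, 0–24 h and 0–7 days), with first-day doses assigned by their recorded clock time. An overnight dose taken before 12 h then counts in the first window. If the diary has no clock-time column for first-day opioid doses, add one.

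If dose times cannot be collected, drop the 12 h opioid value and use 0–24 h as the first window.

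The cost is one sentence in each of the two sections and possibly one diary column. No extra patients, visits or staff are needed. The downside is slightly more writing for the patient on day 1. The change should precede data collection, because doses recorded without a time cannot be reassigned afterwards.
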